1. BACKGROUND

1.1 Epidemiology and burden of the condition

Care of the critically ill typically occurs in the intensive care unit (ICU), although it may commence elsewhere, such as the operating theatre or emergency department. If a patient cannot breathe adequately, they may be assisted by mechanical ventilation. This involves placing a tube into the trachea (endotracheal tube (ETT)), which connects to a ventilator. This system ‘takes over’ breathing for the patient. In the UK, over 60,000 adults receive invasive ventilation each year[1], with most of these surviving to leave hospital (66%)[2]. Mechanical ventilation is known to be associated with some clinically important unwanted effects; one is Ventilator-Associated Pneumonia (VAP). Patients who develop VAP have a protracted ICU stay and worse outcome. In addition to the personal cost and risk for each patient, there are significant healthcare costs associated with a protracted stay on ICU, with each day of care costing around £1500. [3, 4].

VAP is the most common Hospital Acquired Infection (HAI) in ICUs occurring in ~30% of mechanically ventilated patients [5-8]. This increased to 45% during the COVID-19 pandemic.[9] A new class of endotracheal tube aimed at providing advanced airway protection may significantly reduce the incidence of VAP (pneumonia occurring >48 hours after intubation)[10] and in turn the length of mechanical ventilation and stay on ICU. Consequently, reducing VAP incidence is important to patients, clinicians, and policy makers.

The National Institute for Health and Care Excellence (NICE) produced medical technologies guidance 48, (April 2020) [11], highlighting the potential for a new ETT, an advanced airway protection device, to prevent Ventilator Associated Pneumonia[11]. However, the current evidence base is not strong enough for formal NICE approval. Therefore, NICE have recommended definitive research to assess the clinical and cost effectiveness of such advanced airway devices in NHS critical care. NICE have identified the PneuX system as the only current example of an advanced airways protection system, that has the best current evidence for the potential to reduce ventilator associated pneumonia and in turn reduce length of time on a ventilator.

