2.3 Aims and objectives

Objectives:

- (1) Conduct an internal pilot study to confirm the feasibility of a large-scale multicentre trial.
- (2) To conduct a UK-wide multi-centre, open-label, pragmatic, individually randomised, parallel group trial and economic evaluation to determine the clinical and cost effectiveness of an advanced airways protection device versus conventional endotracheal tubes (with and without basic subglottic manual suction and standard cuff) in patients with respiratory failure requiring mechanical ventilation. The outcomes are duration of mechanical ventilation, survival, ICU, and hospital stay outcomes and health-related quality of life.
- (3) Estimate, in an integrated economic evaluation, the cost-effectiveness of an advanced airways protection device versus the conventional endotracheal tubes.

Justification of outcomes

We have worked with patients, the public, researchers and clinicians to determine both our primary and secondary outcomes. This clinical effectiveness trial comprises key core outcomes from the Core Outcomes in Ventilation Trials (COVent) core outcome set and NICE guidelines for ventilation trials and NICE guidelines [5, 12, 13].

Primary effectiveness outcome

The primary variable (outcome) of interest is the duration of mechanical ventilation as measured from time from randomisation to first successful unassisted breathing, measured in days. This outcome is one of the 'COVenT' core outcomes for trials of interventions intended to modify the duration of mechanical ventilation[14]. To clarify:

- Unassisted breathing is defined as no inspiratory support or extracorporeal lung support
- Success is defined as maintaining unassisted breathing at 48 hours.
- Duration includes time receiving extracorporeal lung support, invasive mechanical ventilation and non-invasive ventilation delivering volume or pressure support ventilation.
- Duration excludes time receiving high-flow oxygen therapy and continuous positive airway pressure.
- Patients with a tracheostomy in situ may still achieve successful unassisted breathing.

Secondary outcomes - refer to CoReCCT master protocol for core clinical outcome set.

Effectiveness

- *Duration of endotracheal intubation*: time from randomisation to endotracheal extubation (in hours).
- Ventilator Associated Pneumonia (VAP): Diagnosed by treating clinician with commencement of antibiotics [16] from randomisation up to ICU discharge.

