- Hospital Acquired pneumonia (HAP) following extubation- clinician diagnosis and commencement of antibiotics from randomisation up to ICU discharge.

Safety Outcome Measures

Reportable safety events are described in section 7 of the CoReCCT Master Protocol.

Adverse event rates, including device-related

Adverse event rates related to endotracheal tube intubation within 1 hour of intubation, or tube change if allocated to intervention arm:

- *Traumatic insertion, bleeding*
- *Injury to the throat or trachea*
- *Dental damage*
- *Failed intubation*
- *Aspiration during intubation*
- *Pneumothorax*
- *Obstruction or kinking of the endotracheal tube*
- *Cuff leak*
- *Unintentional extubation*

Adverse event rates related to endotracheal tube intubation after one hour of intubation, or tube change if allocated to intervention arm, up to ICU discharge:

- *Tracheal stenosis*
- *Vocal cord injury / paralysis / Arytenoid dislocation*
- *Hoarse voice / voice changes*
- *Sinusitis*
- *Laryngo-tracheal stenosis*
- *Tracheomalacia*
- *Obstructive fibrinous tracheal pseudo membrane*
- *Pressure injuries related to tube securing or pressure from tracheal tube*

- *Tracheo-oesophageal fistula*
- *C-spine and spinal cord injuries due to intubation*

Patient reported and health-economics outcomes:

- Costs associated with use of NHS & personal social services (PSS) resources arising during hospital stay and after hospital discharge; personal expenditures (out-of-pocket costs) incurred by patients after hospital discharge. (also see section Health Economic Evaluation).
- Health-related quality of life using a widely used and recommended preference-based quality of life instrument (EQ-5D-5L) collected at 2 and 6 months.

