Performance and detection bias (unblinded study): The nature of the trial intervention precludes masking of patients or care providers following randomisation. We will mitigate against potential bias in the absence of blinding, by using an objective measurable primary outcome (duration of mechanical ventilation (days)), and collecting data on intubation and readiness to extubate, and reasons why this might not occur as planned, to confirm consistency across randomised groups and assess performance bias on the part of treating clinicians. Intensive care clinical charts provide contemporaneous, hour by hour records of the patient's physiology and current treatments. Source verification (from clinical records) and hospital computer records will be used to minimise the risk of reporting bias. The main clinical and resource utilisation outcomes of this trial (e.g., ventilation status (hourly); death; level 2/3 care; adverse events, antibiotic uses) are recorded contemporaneously on patient clinical records and hospital information systems. This will enable outcomes to be verified by both site staff and the coordinating centre. It will also not be possible to directly blind the WCTU (Warwick Clinical Trials Unit) trial team to treatment allocation, as this information will be collected on the patient clinical record forms and will be necessary to monitor and manage protocol deviations and compliance/adherence. However, the team will have some blinding regards the randomised intervention, whilst collecting the follow-up outcome data. At the pilot stages, we will assess the patient baseline characteristics at site level, to identify any outliers which may have resulted due to our inability to blind the trial. The trial statistician, who has no role in decision-making with regards the conduct of the trial, will be unblinded and this will also facilitate linkage with the DMC.

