2.11 Blinding

Due to the nature of the trial interventions, it is not possible to blind hospital staff members or patients to treatment allocation.

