Analysis of outcomes: Health-related quality of life (HRQoL) will be measured using the EQ-5D-5L—a widely-used and recommended instrument—at three time points: baseline, 2 months, and 6 months. As it will not be possible for ICU patients to self-complete the baseline EQ-5D-5L questionnaire, baseline EQ-5D indices will be estimated in line with recommendations, assuming that patients are in a particular state determined with PPI input [45]. EQ-5D-5L responses at 2 and 6 months will be converted to preference-based quality of life indices (utility scores) using the UK tariff recommended at the time of analysis (and using alternative tariffs in sensitivity analyses). Quality-adjusted life years (QALYs) will be calculated using the area under the curve (AUC) method and mean per patient QALYs over 6 months will be reported for each trial arm. Sensitivity analyses will be carried out to account for the possibility that changes in HRQoL realised before the first EQ-5D-5L follow-up assessment point (2 months post randomisation) are missed. This will involve attaching HRQoL indices, identified in communication with clinicians and patient representatives, to specific periods related to health status (e.g. remaining in ICU, patient in ward, patient discharged from hospital) using data collected as part of the trial. A secondary analysis will also explore the additional outcome of VAP avoided—a relevant outcome for patients undergoing intubation [10]—on the basis of VAP incidence data collected alongside this trial.

Analysis of cost-effectiveness: The main analysis will be carried out on the basis of patient-level data obtained within the trial follow-up. Incremental analysis will be undertaken to calculate the difference in costs and the difference in

outcomes (QALYs) associated with each of the compared options. Results will be presented in the form of incremental cost-effectiveness ratios (ICER), reflecting the extra cost for an additional unit of outcome. To account for the inherent uncertainty due to sampling variation, the joint distribution of differences in cost and outcomes (QALYs) will be derived by carrying out a large number of non-parametric bootstrap simulations [46]. In line with recommendations, sensitivity analyses will be carried out to explore the impact of uncertain parameters, methods and assumptions[47].

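### VAP is labelled only by unblinded treating clinicians and separated from HAP at extubation, so VAP and cost per VAP avoided can differ between arms without pneumonia being prevented

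*Protocol*

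**What the plan says.** Section 2.3 lists VAP among the secondary effectiveness outcomes: "Ventilator Associated Pneumonia (VAP): Diagnosed by treating clinician with commencement of antibiotics [16] from randomisation up to ICU discharge". It states no radiological, microbiological, physiological or timing criterion. The next outcome has the same structure: "Hospital Acquired pneumonia (HAP) following extubation- clinician diagnosis and commencement of antibiotics from randomisation up to ICU discharge". The VAP line does not mention extubation. The HAP line does, and so makes extubation the boundary between the two.

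Section 2.11 says that "it is not possible to blind hospital staff members or patients to treatment allocation". Section 2.10 adds of the coordinating team: "It will also not be possible to directly blind the WCTU (Warwick Clinical Trials Unit) trial team to treatment allocation". Its answer to performance and detection bias begins: "We will mitigate against potential bias in the absence of blinding, by using an objective measurable primary outcome (duration of mechanical ventilation (days". It goes on to the collection of data on readiness to extubate, and to source verification of contemporaneous records, antibiotic use among them.

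VAP also enters the economic evaluation. Section 6.5 says: "A secondary analysis will also explore the additional outcome of VAP avoided". It uses the trial's own VAP data and will present the result as additional cost per VAP avoided. The main economic result is cost per QALY.

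**The concern.** Preventing VAP is the mechanism by which the device is expected to work. Section 1.1 says the new class of tube may "reduce the incidence of VAP (pneumonia occurring >48 hours after intubation" and, through that, shorten ventilation. A clinician who knows that the patient has this tube may be slower to call a new infiltrate or fever VAP, or readier to do so with a standard tube. Either habit lowers the recorded device-to-control ratio. The antibiotic requirement is no independent check, because the same unblinded team orders the antibiotics.

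The second route needs no bias in judgement. If the device does shorten intubation, a pneumonia that would have appeared before extubation in the control arm may appear after it in the device arm. It is then HAP, and the VAP count falls by one although the patient still had pneumonia.

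At stake are the reading of the VAP result and the cost per VAP avoided built on it. The primary outcome is not at stake.

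**Working it through.** **Do the section 2.10 safeguards reach VAP?**

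- Objective primary outcome: it protects duration of ventilation. VAP is a different variable.
- Readiness-to-extubate data: these too concern duration of ventilation.
- Source verification: it can confirm that a diagnosis was written and an antibiotic started. It cannot show whether the same patient with the other tube would have had the same diagnosis or order.

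The protocol describes no allocation-blind assessment of VAP and no objective criterion for it.

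**The plan's own sample size.** The trial is sized on duration of ventilation. With HR = 1.2^0.901 = 1.1785, two-sided 5% alpha (sidedness assumed) and 90% power, Freedman's formula gives events = (1.960 + 1.282)² × [(1.1785 + 1)/(1.1785 − 1)]² ≈ 1565. Inflating for 25.6% mortality and 3% withdrawal gives 1565/(1 − 0.256 − 0.03) = 2192, against the stated 2194. The size is not in dispute. No effect size or power is given for VAP.

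**What 1097 per arm can show for VAP.** From a 30% rate (section 1.1), the detectable absolute difference is about 5.3 points at 80% power and 6.1 points at 90%.

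**Illustration of under-labelling.** Inputs: n = 1097 per arm (section 6.1); true VAP rate 30% in both arms (section 1.1); a fraction f of device-arm episodes left unlabelled. The documents give no value for f, so every value is an assumption. The recorded device-arm rate is p₂ = 0.30(1 − f), and d = 0.30 − p₂. The chance of a two-sided p < 0.05 is Φ[(d − 1.96·SE₀)/SE₁], where SE₀ is the pooled and SE₁ the unpooled standard error.

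For f = 10%: p₂ = 0.27 and d = 0.03. SE₀ = √(2 × 0.285 × 0.715/1097) = 0.01928. SE₁ = √((0.30 × 0.70 + 0.27 × 0.73)/1097) = 0.01926. (0.03 − 0.03778)/0.01926 = −0.40, and Φ(−0.40) ≈ 0.34.

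| f (assumed) | Recorded rates | OR | Chance of false significance | Episodes falsely avoided (1097 × d) |
|---|---|---|---|---|
| 5% | 28.5% v 30% | 0.93 | 12% | 16 |
| 10% | 27.0% v 30% | 0.86 | 34% | 33 |
| 15% | 25.5% v 30% | 0.80 | 65% | 49 |

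The base rate matters. For f = 5%, 10% and 15%, the chances are 7%, 17% and 33% at an assumed 15% VAP rate, and 19%, 57% and 89% at the 45% that section 1.1 gives for the pandemic. Removing 3% for withdrawal (1064 per arm) changes the 30% figures only to about 12%, 34% and 64%. This is an unadjusted two-proportion approximation to the planned mixed-effects logistic model.

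**Illustration of movement at extubation.** At 30%, the device arm would have 1097 × 0.30 = 329 patients with VAP. If 33 of them had the same pneumonia after extubation instead, recorded VAP would be 296/1097 = 27.0% against 30%, the same apparent benefit as in the 10% row. HAP would rise by 33, and the number with any pneumonia would not change. The figure of 33 is chosen only to match that row.

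**The case against.** The case for leaving this alone has substance. The trial is pragmatic, and clinician diagnosis plus antibiotics is a deliberate choice with a reference. VAP is secondary and does not appear among the outcomes listed in objective 2 of section 2.3. The cost-per-VAP-avoided analysis is explicitly exploratory. Antibiotic use is recorded at the time and can be verified, so a fall in VAP with no fall in antibiotic use or ventilation would be visible. HAP is reported separately over the same window, so movement between the two would also be visible. Some fall in VAP through less time on the ventilator is a real benefit. The SAP, the CoReCCT master protocol and the Health Economics Analysis Plan are not at hand and could contain supporting definitions.

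Most of this limits the size of the point and does not answer it. Verifying an antibiotic order does not make the decision to order it independent of the tube. Separate HAP reporting shows movement only to a reader who adds the two outcomes together, and the planned economic measure counts VAP alone. The protocol itself fixes both the definition and the defence against open-label bias, and it points to nothing elsewhere that covers VAP.

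**Conclusion.** The point holds for a secondary outcome and a secondary economic analysis. As defined, a lower VAP rate with the device could reflect prevention, differential labelling, movement of episodes to HAP, or a mixture. At 30% and 1097 per arm, under-labelling of 5% to 15% gives a false significant benefit in about 12% to 65% of trials. Those fractions are assumptions, and the documents establish neither the size nor the direction of any bias.

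Four stronger readings are tempting and are not supported:

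- **The trial's main conclusions are compromised.** The primary outcome does not use the VAP label, and the main economic result is cost per QALY.
- **The outcome contradicts the 48-hour definition in section 1.1.** The outcome line can be read as an ascertainment window that leaves the usual definition in place. The missing detail applies to both arms and shows no between-arm bias.
- **Antibiotics already running at baseline bias the comparison.** They may cost sensitivity, but this too applies to both arms alike.
- **Clinicians are trained to expect less VAP with the device.** Section 2.6 describes training in handling the device and does not say that it is presented there as preventing VAP.

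**What to change.** 1. Keep the clinician definition of VAP.
2. Add any pneumonia (VAP or HAP) from randomisation to ICU discharge, counted once per patient, and report it beside VAP. It is derived from data already collected and removes the effect of the boundary at extubation. It does not remove labelling bias, since HAP rests on the same kind of diagnosis.
3. Repeat the cost-per-VAP-avoided analysis as cost per pneumonia avoided and present the two together.
4. As a sensitivity analysis only, report VAP under a rule set in advance and computed without allocation, from recorded intubation times, antibiotic records and whatever oxygenation or ventilator data are already captured.
5. State in the plan that a VAP difference not supported by these measures will be read as open to detection bias.

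The cost is a little more analysis, with no new procedures or adjudicators. The rule still depends partly on antibiotic orders made by unblinded staff, so it reduces the bias without removing it. For that reason it should not replace the clinician definition as the basis for conclusions.

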2.5 Participant identification / Screening

Staff will identify potential participants in appropriate clinical areas, such as emergency departments, critical care units, acute wards, operating theatres. Potential processes for identifying patients include referrals, screening in clinical areas, or review of electronic health systems using appropriate queries. We will work with each participating site to support the development of strategies to optimise screening in their hospital.

Screening information will be entered on to a trial web application, hosted by Warwick Clinical Trials Unit (WCTU). This will capture anonymised data on the numbers of patients meeting inclusion criteria for the trial but not entered into the trial along with the reasons for non-enrolment. These data are important to understand the generalisability of the recruited patient population.

Screening of patients will involve reviewing personal identifiable information. This may be undertaken by a member of the patient's existing clinical care team, or by a member of the hospital research team, depending on local arrangements. Screening and eligibility assessment may be undertaken by any individual clinically competent to undertake that role, as determined by the principal investigator. It is anticipated that this process may be undertaken at any time of day or night, provided appropriately trained staff members are available.

Patients who need intubating, or who have been intubated within the last 24 hours prior to randomisation are eligible for the trial. Confirmation that all eligibility criteria are met will be entered on to the trial web application prior to the patient being randomised.

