2.8 Randomisation

2.8.1 Randomisation

A bespoke online randomisation system will be developed, by the WCTU programming team. The system will be based on a computerised algorithm using the minimisation method for randomising patients. The randomisation sequence will be created, stratified by hospital site, if the patient is intubated prior to randomisation and prior enrolment into the Awake Prone trial. Patients will be randomised, in a ratio of 1:1 to the advanced airways protection device or the standard of care endotracheal tube (with or without the basic subglottic suction/standard cuff). Randomisation can happen up to 24 hours after primary intubation. **If randomised to the intervention arm, this may necessitate a tube change. The tube change should occur within 24 hours of the patient initially being intubated.**

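### The VAP outcome sets no minimum time from intubation and no end to attribution, so early pneumonia can be recorded as VAP and one post-extubation pneumonia can meet both the VAP and HAP definitions

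*Protocol*

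**What the plan says.** Section 1.1 of the Protocol, in setting out the rationale, describes VAP as "pneumonia occurring >48 hours after intubation".

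Section 2.3 lists VAP among the secondary effectiveness outcomes: "Ventilator Associated Pneumonia (VAP): Diagnosed by treating clinician with commencement of antibiotics [16] from randomisation up to ICU discharge". The next item is "Hospital Acquired pneumonia (HAP) following extubation- clinician diagnosis and commencement of antibiotics from randomisation up to ICU discharge".

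Three other statements fix when the outcome window opens relative to intubation:
- Section 2.5: "Patients who need intubating, or who have been intubated within the last 24 hours prior to randomisation are eligible for the trial".
- Section 2.8.1: "Randomisation can happen up to 24 hours after primary intubation".
- Section 2.8.1, for the intervention arm where a change of tube is needed: "The tube change should occur within 24 hours of the patient initially being intubated".

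Section 2.10 states that care providers cannot be masked. VAP is used again in section 6.5: "A secondary analysis will also explore the additional outcome of VAP avoided". Results there are also to be expressed as cost per VAP avoided.

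**The concern.** The background gives VAP a time threshold measured from intubation. The outcome gives it a window measured from randomisation, with no threshold. The two clocks differ, and the outcome window always opens inside the first 48 hours after intubation, or before intubation. Pneumonia already present or incubating when the tube was placed can therefore enter the VAP count.

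The window also has no end tied to extubation or to the end of ventilation. HAP is confined to after extubation, yet its stated window starts at randomisation, which does not fit that restriction. Between extubation and ICU discharge both definitions apply, and no rule assigns an episode to one of them.

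VAP is the mechanism by which section 1.1 expects the device to shorten ventilation, and it is the effect measure in the cost per VAP avoided. The diagnosis is made by treating clinicians who know the allocation. The protocol's stated safeguard against lack of blinding is an objective primary outcome, which does not protect this outcome. Without a time rule, labelling is left to individual judgement across the 44 planned sites.

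**Working it through.** **1. The protocol's own figures.** No expected rate, power or sample size is stated for VAP as an outcome, so there is no VAP figure to reproduce. The trial size rests on the primary outcome and can be recovered. The hazard ratio adjusted for the Weibull shape is 1.2^0.901 = 1.1785. Freedman's formula, with two-sided 5% alpha (sidedness assumed) and 90% power, gives 1565 events. Then 1565 / (1 − 0.256 − 0.03) = 2192, against the stated 2194. VAP does not enter that calculation.

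**2. Length of window before the threshold.** Let r be the hours from first intubation to randomisation. The part of the window lying within 48 hours of intubation is 48 − r.

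| Randomised | Hours of window before the 48-hour threshold |
|---|---|
| Before intubation | more than 48 |
| At intubation (r = 0) | 48 |
| r = 12 | 36 |
| r = 24 (the limit) | 24 |

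**3. Overlap of VAP and HAP.**

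| Period | VAP wording met? | HAP wording met? |
|---|---|---|
| Randomisation to extubation | yes | no (restricted to after extubation) |
| Extubation to ICU discharge | yes (no end stated) | yes |

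The overlap arises because VAP has no end point.

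**4. Illustration of dilution when early cases are balanced.** Only the 30% control rate comes from the protocol (section 1.1). The true risk ratio of 0.70, the early-pneumonia proportion e, and the labelling of every early case as VAP are assumptions.

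Observed risk = e + (1 − e) × p, with p = 0.30 (control) and 0.30 × 0.70 = 0.21 (device).

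| e, both arms | Control | Device | Observed risk ratio | Absolute reduction (points) |
|---|---|---|---|---|
| 0 | 0.300 | 0.210 | 0.70 | 9.0 |
| 0.05 | 0.335 | 0.2495 | 0.74 | 8.55 |
| 0.10 | 0.370 | 0.289 | 0.78 | 8.1 |
| 0.15 | 0.405 | 0.3285 | 0.81 | 7.65 |

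At a fixed incremental cost, cost per VAP avoided rises by 9.0/8.55, 9.0/8.1 and 9.0/7.65, that is by about 5%, 11% and 18%. Power at 1097 per arm stays high (0.998 falling to 0.993, 0.981 and 0.961).

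The loss is larger for a smaller effect. If a share s of the 30% counted as VAP is unaffected by the device, the observed risk ratio is s + (1 − s) × RR. With an assumed RR of 0.80 and s = 10%, 20% or 30%, it becomes 0.82, 0.84 or 0.86. Power falls from 0.89 to 0.81, 0.71 or 0.59.

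**5. Illustration when early cases are unbalanced.** With the same formula, e = 0.05 in control and 0.10 in device gives 0.289 / 0.335 = 0.86. With e = 0.10 in control and 0.05 in device the result is 0.2495 / 0.370 = 0.67. The first weakens the assumed effect of 0.70 and the second exaggerates it.

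**The case against.** The best defence is that the two sections can be read together. What the clinician must diagnose is VAP, section 1.1 says what VAP is, and section 2.3 adds who diagnoses it, the treatment criterion and the observation period. On that reading the shared window only says when data are collected. Antibiotics must also be commenced, so pneumonia already under treatment at randomisation does not qualify on that course, and antibiotic receipt is a baseline item (section 6.2.3). Hourly ventilation status and antibiotic use are charted (section 2.10), so timing may be recoverable. The case report form and the CoReCCT master protocol are not shown, so it cannot be said that an onset time is not collected.

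Much of this stands, and it limits the point. A reader might infer that every early pneumonia will count as VAP. The documents do not support that: a clinician may apply a 48-hour convention, so early cases can count but need not. It does not remove the point, because the threshold appears only in a background parenthesis, section 2.3 does not adopt it, and nothing requires sites to apply it.

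A reader might also infer that the extra cases are ones the tube could neither cause nor prevent. That is plausible for pneumonia present or incubating at intubation, but not in general. Pneumonia after extubation may follow micro-aspiration while the tube was in place, so the overlap is a problem of classification and double counting. Pneumonia after aspiration at a tube change would be a consequence of the allocated strategy. Aspiration during intubation, including at a tube change, is separately listed as a safety outcome.

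**Conclusion.** The point holds as an outcome-definition fault for a secondary outcome. The section 2.3 window includes at least 24 hours, and often 48 or more, that precede the protocol's own threshold, and it lets one post-extubation pneumonia meet both the VAP and HAP wording. This follows from the text alone.

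The size of the effect is not known from the documents. If early cases are balanced, they pull the VAP comparison towards no difference and raise the cost per VAP avoided. The range of about 0.74 to 0.81 for an assumed true risk ratio of 0.70 is illustrative and requires every early case to be labelled VAP. A general conclusion that the VAP result is biased towards the null would go too far. Only the device arm may need a protocol-driven tube change and the diagnosis is unblinded, so early cases may be unbalanced and the direction is then uncertain. The primary outcome and the sample size of 2194 are unaffected.

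**What to change.** In section 2.3:
- Align the VAP outcome with section 1.1 by requiring onset more than 48 hours after first intubation, timed from intubation and not from randomisation. Keep the clinician diagnosis and antibiotic criteria.
- State when VAP attribution ends, and say explicitly how re-intubation and continued ventilation by tracheostomy are handled. A bare cut-off at extubation would misclassify pneumonia in patients still or again ventilated.
- Start the HAP window at extubation, and assign each pneumonia episode to one category only.
- Record the onset date and time of each episode, and report pneumonia before the threshold separately, by arm.

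Use the same definition for VAP avoided in section 6.5.

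The cost is a wording change, a somewhat lower VAP count and, if not already captured, an onset-time field on the case report form. Collecting it prospectively avoids reconstructing onset from charts later.
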